8.6.2 Statistical Methods for Safety Analyses

Safety and tolerability will be assessed by clinical review of all relevant parameters including adverse experiences (AEs), laboratory tests, vital signs, etc.

The analysis of safety results will follow a tiered approach (Table 17). The tiers differ with respect to the analyses that will be performed. Safety parameters or adverse experiences of special interest that are identified *a priori* constitute “Tier 1” safety endpoints that will be subject to inferential testing for statistical significance with p-values and 95% confidence intervals provided for between-group comparisons. Other safety parameters will be considered Tier 2 or Tier 3. Tier 2 parameters will be assessed via point estimates with 95%

confidence intervals provided for between-group comparisons; only point estimates by treatment group are provided for Tier 3 safety parameters. No formal treatment comparisons with p-values will be carried out.

Adverse experiences (specific terms as well as system organ class terms) and predefined limits of change in laboratory, vital signs, and ECG parameters will be classified as belonging to "Tier 2" or "Tier 3", based on the number of events observed. Membership in Tier 2 requires that at least 4 subjects in any treatment group exhibit the event; all other adverse experiences and predefined limits of change will belong to Tier 3.

The threshold of at least 4 events was chosen because the 95% confidence interval for the between-group difference in percent incidence will always include zero when treatment groups of equal size each have less than 4 events and thus would add little to the interpretation of potentially meaningful differences. Because many 95% confidence intervals may be provided without adjustment for multiplicity, the confidence intervals should be regarded as a helpful descriptive measure to be used in review, not a formal method for assessing the statistical significance of the between-group differences in adverse experiences and predefined limits of change.

Continuous measures such as changes from baseline in laboratory, vital signs, and ECG parameters will be considered Tier 3 safety parameters. Summary statistics for baseline, on-treatment, and change from baseline values will be provided by treatment group in table format.

For this protocol, there are no Tier 1 events. In addition, the broad clinical and laboratory AE categories consisting of the percentage of subjects with any AE, any drug related AE, any serious AE, any Grade 3-5 AE, an AE which is both Grade 3-5 and drug-related, an AE which is both drug-related and serious, dose modification due to AE, and who discontinued due to an AE, and death will be considered Tier 2 endpoints. 95% confidence intervals (Tier 2) will be provided for between-treatment differences in the percentage of subjects with events; these analyses will be performed using the Miettinen and Nurminen method (1985) [55], an unconditional, asymptotic method.

To properly account for the potential difference in follow-up time between the study arms, which is expected to be longer in the pembrolizumab containing arms, AE incidence density adjusted for treatment exposure analyses may be performed as appropriate. Based on emerging external data, the supportive analysis strategy for safety parameters may be modified to improve the integrity and efficiency of the design. Should this happen, the change will be documented in supplemental SAP, if not in a protocol amendment, at the earliest time before any unblinding of the data.

Table 17 Analysis Strategy for Safety Parameters

Safety Tier	Safety Endpoint	95% CI for Treatment Comparison	Descriptive Statistics
Tier 2	Any AE	X	X
	Any Grade 3-5 AE	X	X
	Any Serious AE	X	X
	Any Drug-Related AE	X	X
	Any Serious and Drug-Related AE	X	X
	Any Grade 3-5 and Drug-Related AE	X	X
	Dose Modification due to AE	X	X
	Discontinuation due to AE	X	X
	Death	X	X
	Specific AEs, SOCs (including ≥ 4 subjects in one of the treatment groups)	X	X
Tier 3	Specific AEs, SOCs (incidence < 4 subjects in all of the treatment groups)		X
	Change from Baseline Results (Labs, ECGs, Vital Signs)		X
† Adverse Experience references refer to both Clinical and Laboratory AEs. Note: SOC=System Organ Class; X = results will be provided.			

Time to Grade 3-5 AE

In addition to tiered approach, exploratory analysis will be performed on time to first Grade 3-5 AE. Time to first Grade 3-5 AE is defined as the time from the first day of study drug to the first event of Grade 3-5 AE. The Kaplan-Meier method will be used to estimate the curve of time to first Grade 3-5 AE. The treatment difference in time to first Grade 3-5 AE will be assessed by the unstratified log-rank test. An unstratified Cox proportional hazards model with Efron's method of tie handling will be used to assess the magnitude of the treatment difference (i.e., the hazard ratio). The hazard ratio and its 95% confidence interval from the unstratified Cox model with a single treatment covariate will be reported. More details will be described in supplemental SAP.

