7.2 Assessing and Recording Adverse Events

An adverse event is defined as any untoward medical occurrence in a patient or clinical investigation subject administered a pharmaceutical product and which does not necessarily have to have a causal relationship with this treatment. An adverse event can therefore be any unfavourable and unintended sign (including an abnormal laboratory finding, for example), symptom, or disease temporally associated with the use of a medicinal product or protocol-specified procedure, whether or not considered related to the medicinal product or protocol-specified procedure. Any worsening (i.e., any clinically significant adverse change in frequency and/or intensity) of a preexisting condition that is temporally associated with the use of the Sponsor's product, is also an adverse event.

Changes resulting from normal growth and development that do not vary significantly in frequency or severity from expected levels are not to be considered adverse events. Examples of this may include, but are not limited to, teething, typical crying in infants and children and onset of menses or menopause occurring at a physiologically appropriate time.

Sponsor's product includes any pharmaceutical product, biological product, device, diagnostic agent or protocol-specified procedure, whether investigational (including placebo or active comparator medication) or marketed, manufactured by, licensed by, provided by or distributed by the Sponsor for human use.

Adverse events may occur during clinical trials, or as prescribed in clinical practice, from overdose (whether accidental or intentional), from abuse and from withdrawal.

Progression of the cancer under study is not considered an adverse event.

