All adverse events that occur after the consent form is signed but before treatment allocation/randomization must be reported by the investigator if they cause the subject to be excluded from the trial, or are the result of a protocol-specified intervention, including but not limited to washout or discontinuation of usual therapy, diet, placebo treatment or a procedure. From the time of treatment allocation/randomization through 30 days following cessation of treatment, all adverse events must be reported by the investigator. Such events will be recorded at each examination on the Adverse Event case report forms/worksheets. The reporting timeframe for adverse events meeting any serious criteria is described in section 7.2.3.1. The investigator will make every attempt to follow all subjects with non-serious adverse events for outcome.

Electronic reporting procedures can be found in the EDC data entry guidelines. Paper reporting procedures can be found in the Investigator Trial File Binder (or equivalent).

Adverse events will not be collected for subjects during the pre-screening period (for determination of archival tissue status) as long as that subject has not undergone any protocol-specified procedure or intervention. If the subject requires a blood draw, fresh tumor biopsy etc., the subject is first required to provide consent to the main study and AEs will be captured according to guidelines for standard AE reporting.

7.2.1 Definition of an Overdose for This Protocol and Reporting of Overdose to the Sponsor

For purposes of this trial, an overdose will be defined as any dose exceeding the prescribed dose for pembrolizumab defined as any dose greater than 1000 mg or greater. For lenalidomide or dexamethasone an overdose will be defined as any dose that is considered both excessive and medically important by local standards. No specific information is available on the treatment of overdose of pembrolizumab, lenalidomide or dexamethasone. In the event of overdose, pembrolizumab, lenalidomide or dexamethasone should be discontinued and the subject should be observed closely for signs of toxicity. Appropriate supportive treatment should be provided if clinically indicated.

If an adverse event(s) is associated with (“results from”) the overdose of Sponsor's product or vaccine, the adverse event(s) is reported as a serious adverse event, even if no other seriousness criteria are met.

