7.2.3 Immediate Reporting of Adverse Events to the Sponsor

7.2.3.1 Serious Adverse Events

A serious adverse event is any adverse event occurring at any dose or during any use of Sponsor's product that:

- Results in death;
- Is life threatening;
- Results in persistent or significant disability/incapacity;
- Results in or prolongs an existing inpatient hospitalization;
- Is a congenital anomaly/birth defect;
- Is an other important medical event.

Note: In addition to the above criteria, adverse events meeting either of the below criteria, although not serious per ICH definition, are reportable to the Sponsor in the same timeframe as SAEs to meet certain local requirements. Therefore, these events are considered serious by the Sponsor for collection purposes.

- Is a new cancer (that is not a condition of the study);
- Is associated with an overdose.

Refer to [Table 14](#) for additional details regarding each of the above criteria.

For the time period beginning when the consent form is signed until treatment allocation/randomization, any serious adverse event, or follow up to a serious adverse event, including death due to any cause, other than progression of the cancer under study (reference Section 7.2.3.3 for additional details) that occurs to any subject must be reported within 24 hours to the Sponsor if it causes the subject to be excluded from the trial, or is the result of a protocol-specified intervention, including but not limited to washout or discontinuation of usual therapy, diet, placebo treatment or a procedure.

For the time period beginning at treatment allocation/randomization through 90 days following cessation of treatment, or 30 days following cessation of treatment if the subject initiates new anticancer therapy, whichever is earlier, any serious adverse event, or follow up to a serious adverse event, including death due to any cause, other than progression of the cancer under study (reference Section 7.2.3.3 for additional details) whether or not related to the Sponsor's product, must be reported within 24 hours to the Sponsor either by electronic media or paper. Electronic reporting procedures can be found in the EDC data entry

guidelines. Paper reporting procedures can be found in the Investigator Trial File Binder (or equivalent).

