8.9 Sample Size and Power Calculations

The study will randomize approximately 640 subjects in a 1:1 ratio among the two treatment arms: pembrolizumab in combination with SOC (combination therapy), and SOC (control).

The interim PFS analysis will be performed after approximately 115 PFS events accrue, this will occur ~20 months after the first subject is enrolled.

If the PFS null hypothesis is neither accepted nor rejected at the time of the interim analysis, then a final PFS analysis will be conducted after approximately 227 PFS events have been observed in the trial.

An OS analysis will be performed after approximately 195 deaths have occurred.

The primary endpoint of the study is PFS. The study has ~90% power to detect a hazard ratio of 0.65 (pembrolizumab in combination with SOC vs. SOC) at alpha = 2.5% (one-sided). The sample size calculation is based on the following assumptions: 1) progression-free survival follows an exponential distribution with a median of 25.5 months in the control arm, 2) an enrollment period of 18 months and at least 12 months follow-up, and 3) a cumulative dropout rate of 2% at the end of the first year and 5% at 4 years.

The secondary endpoint of the study is OS. Assuming that the PFS null hypothesis is rejected, the study has ~70% power to detect a hazard ratio of 0.70 (pembrolizumab in combination with SOC vs. SOC) at $\alpha = 2.5\%$ (one-sided). These calculations are based on the following assumptions: 1) OS follows an exponential distribution with 70% overall survival at 36 months in the control arm (Arm B), 2) an enrollment period of 18 months and at least 38 months follow-up, and 3) the same dropout rate as above.

The assumed median PFS and OS in the control arm (Arm B) are observed from standard of care in patients with previously untreated multiple myeloma who are ineligible for SCT [39].

The sample size and power calculations were performed using EAST 6 software.

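### The exploratory Kaplan-Meier curve for time to first Grade 3-5 AE has no state for a death that is not an AE, so it modestly overstates the share of subjects affected

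*Combined protocol and SAP*

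**What the plan says.** Section 8.6.2, under Time to Grade 3-5 AE, states that "exploratory analysis will be performed on time to first Grade 3-5 AE". The endpoint is "defined as the time from the first day of study drug to the first event of Grade 3-5 AE". On the estimator it says: "The Kaplan-Meier method will be used to estimate the curve of time to first Grade 3-5 AE". The arms are compared by an unstratified log-rank test and an unstratified Cox model. No censoring rule, competing event or handling of death is given, and the paragraph ends: "More details will be described in supplemental SAP".

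The safety sections settle which deaths can count:

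- Section 7.2: "Progression of the cancer under study is not considered an adverse event".
- Section 7.2.3.1 requires SAE reports "including death due to any cause, other than progression of the cancer under study", and section 7.2.3.3 repeats the exception.
- Table 14 (section 7.2.4) reserves Grade 5 for deaths related to an AE.

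On collection, section 7.2 says that "through 30 days following cessation of treatment, all adverse events must be reported by the investigator". SAEs are collected to 90 days (30 if new anticancer therapy starts), and SAEs judged related to the product are reportable at any time (section 7.2.3.1).

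Table 17 separately lists the percentage of subjects with any Grade 3-5 AE as a Tier 2 endpoint, with a confidence interval for the arm difference.

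**The concern.** Kaplan-Meier recognises two outcomes: the event, and censoring. Censoring assumes that the subject could still have the event later, at the same rate as those who remain at risk. That cannot be true of a subject who has died of myeloma without a Grade 3-5 AE. The estimator redistributes that subject's probability over those still at risk, so one minus the curve describes a setting in which nobody dies of myeloma. It is not the proportion of treated subjects who have a severe AE by a given time.

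Readers usually take such a curve as that proportion. This is the only time-to-event analysis of AEs in section 8.6.2, in a trial whose treatment phase was closed on safety data, so the absolute level will be read.

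**Working it through.** **1. Design inputs.** The plan gives no figure for this endpoint, so only its design figures can be reproduced.
- PFS events for hazard ratio 0.65, 90% power, one-sided 2.5%: 4 × (1.960 + 1.282)² / (ln 0.65)² = 226.5, or 227 as stated.
- Deaths at 56 months (640 subjects, 18 months' uniform accrual, 70% control survival at 36 months, hazard ratio 0.70, the stated dropout): 200 to 203 expected, against 195 stated.

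The survival assumption is therefore usable.

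**2. Death hazard.** Section 8.9 assumes exponential OS with 70% alive at 36 months in the control arm: m = −ln(0.70)/36 = 0.0099 per month. This is an upper bound for the competing hazard. It includes AE-related deaths, which are Grade 5 events here, and deaths after AE collection has ended.

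**3. Curve against share affected.** Let a be the hazard of a first Grade 3-5 AE.
- Kaplan-Meier target: 1 − exp(−a·t)
- Share affected: a/(a+m) × [1 − exp(−(a+m)·t)]
- Standard error of the curve (Greenwood, n = 320 per arm, no other censoring before t): exp(−a·t) × √{ a/(a+m) × [exp((a+m)·t) − 1] / 320 }

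Example for 50% at 12 months: a = ln 2/12 = 0.0578; share = 0.0578/0.0677 × [1 − exp(−0.812)] = 0.854 × 0.556 = 47.5%.

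| Assumed 12-month risk (1 − KM) | a per month | Share affected | Excess, points | Excess in SE |
|---|---|---|---|---|
| 50% | 0.0578 | 47.5% | 2.5 | 0.9 |
| 60% | 0.0764 | 57.1% | 2.9 | 1.0 |
| 70% | 0.1003 | 66.8% | 3.2 | 1.2 |
| 80% | 0.1341 | 76.6% | 3.4 | 1.5 |

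The risk is an assumption. The nearest figure in the documents is 23 of 50 subjects (46%) with a Grade 3-4 treatment-related AE in the relapsed/refractory study (section 4.2.2.2). At 46% the excess is 2.4 points; at 20% it is 1.1.

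**4. End of AE collection, examined separately.** The plan assumes that "progression-free survival follows an exponential distribution with a median of 25.5 months in the control arm", which gives a PFS-event hazard of ln 2/25.5 = 0.0272 per month in Arm B and 0.65 × 0.0272 = 0.0177 in Arm A. Suppose observation stops one month after a PFS event (all PFS events treated as progressions). With m now this hazard, the share with an AE inside the collection window is

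1 − exp(−a) + a·exp(m)/(a+m) × [exp(−(a+m)) − exp(−(a+m)·t)].

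For 12-month risks of 50% to 80%, one minus Kaplan-Meier exceeds this window share at 12 months by 5.4 to 7.1 points in B and 3.6 to 4.7 in A. Without the one-month lag the figures are 6.5 to 8.9 and 4.4 to 5.9.

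The result changes if the target is AEs regardless of treatment stop. With 46% risk at 12 months, simulation at 24 months gives:
- one minus Kaplan-Meier 70.8%, window share 56.9%;
- share had collection continued: 65.3%, 70.8% or 74.5% if the AE hazard after the window is 0.5, 1 or 1.5 times the earlier one;
- with a shared frailty for AEs and progression (variance 0.5), Kaplan-Meier 58.4% against a true 61.7%.

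For that target the curve can be too high, right or too low.

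**The case against.** The defence has several good points.

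- **The share is already reported.** Table 17 gives the crude percentage with a Grade 3-5 AE by arm. This stands and lowers the importance. The percentage has no time axis, however, so it does not correct the curve.
- **Exploratory status and missing detail.** The text does not say that myeloma deaths are censored; that follows from the method named. The supplemental SAP, which is not among the documents, may state a rule. This also stands, but plain Kaplan-Meier offers no other treatment of such a death.
- **The test and the model are sound.** Log-rank and Cox compare cause-specific hazards validly when competing deaths are censored. The point concerns the curve only.

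A reader might go further and infer that the end of AE collection after progression also inflates the curve, by 6 to 9 points in Arm B and less in Arm A. The documents do not support that as a general statement. Collection ends after treatment stops for any reason, serious events are collected for longer, and Arm A may be treated beyond progression (section 7.1.2.8.6). A severe AE remains possible after collection ends; it is simply not observed. The overstatement holds only if the target is AEs inside the collection window, and the plan names no target.

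A reader might also cite 24-month gaps of 15 to 16 points in B, or an arm distortion of about 5 points. These rest on the same window target and on the design hazard ratio of 0.65, and they do not fit the halted trial. From the original protocol (28-JUL-2015) to the clinical hold (03-JUL-2017) is 706 days, or 23.2 months, and 24.2 with the 30-day window. Practically nobody is observed for general AEs to month 24.

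**Conclusion.** The point holds in a limited form. One minus the Kaplan-Meier curve overstates the share with a first Grade 3-5 AE whenever a subject under observation dies of something that is not an AE before having one. The direction is certain if such deaths are censored, as the named method implies. The size is at most about 2.5 to 3.4 points at 12 months, or 0.9 to 1.5 standard errors with 320 per arm. That bound assumes a 12-month AE risk of 50% to 80%, constant hazards and the plan's control-arm OS. It is generous because it counts every death as competing; most deaths that follow progression would come after AE collection had already ended. Actual mortality by arm could differ from the plan's assumption.

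No fixed direction can be claimed for the end of AE collection until the target is stated. Importance is low to moderate.

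**What to change.** In section 8.6.2, or in the supplemental SAP to which it refers:

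1. Report the Aalen-Johansen cumulative incidence of first Grade 3-5 AE by arm with 95% confidence intervals, in place of or beside the Kaplan-Meier curve. Treat a non-AE death without a prior Grade 3-5 AE as a competing event.
2. State the censoring times: end of the AE collection window, data cutoff or loss to follow-up. Stops under the 03-JUL-2017 closure are censored at the end of their window. Say which window applies, since serious events are collected for longer.
3. State the target. If it is AEs inside the on-treatment collection window, add a version in which a treatment stop for progression, plus the 30-day window, is a competing event.
4. Keep the log-rank test and the Cox model, and label the Cox estimate a cause-specific hazard ratio.

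The cost is SAP wording and a standard procedure; no new data are needed. Section 8.0 already allows the analysis to be modified and reported in the CSR. The drawback is a slightly lower curve that cannot be compared directly with Kaplan-Meier curves from related trials. Showing both curves avoids that.

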5.2.1.2.3 Dose Modification Guidelines for Dexamethasone

Low-dose dexamethasone will be given at 40 mg once orally on Days 1, 8, 15, and 22 (i.e., once weekly) of repeated 28-day cycles every 28 days. For subjects aged > 75 years in both arms, a daily dexamethasone dose of 20 mg on days 1, 8, 15, and 22 every 28 days is recommended [39].

The criteria presented in this section for dose modification are meant as general guidelines, and they are based on current US standards of clinical practice. Local standards and

prescribing information may differ and should be followed. Dexamethasone dose modifications for toxicity must be performed as clinically indicated at the discretion of the investigator. Refer to the dexamethasone local prescribing information, [Table 7](#), and [Table 8](#) for dose modification guidelines.

Table 7 Supportive Care Guidelines Specific to Dexamethasone

Body System	Symptom	Recommended Action
Gastrointestinal	Dyspepsia, gastric or duodenal ulcer, gastritis Grade 1–2 (requiring medical management)	Treat with H2 blockers, sucralfate, or omeprazole. If symptoms persist despite above measures, decrease dexamethasone dose by one dose level.
Gastrointestinal	> Grade 3 (requiring hospitalization or surgery)	Hold dexamethasone until symptoms adequately controlled. Restart and decrease one dose level of current dose along with concurrent therapy with H2 blockers, sucralfate, or omeprazole. If symptoms persist despite above measures, discontinue dexamethasone and do not resume.
Gastrointestinal	Acute pancreatitis	Discontinue dexamethasone and do not resume.
Cardiovascular	Edema >Grade 3 (limiting function and unresponsive to therapy or anasarca)	Diuretics as needed, and decrease dexamethasone dose by one dose level; if edema persists despite above measures, decrease dose another dose level. Discontinue dexamethasone and do not resume if symptoms persist despite second reduction.
Neurology	Confusion or Mood alteration > Grade 2 (interfering with function +/- interfering with activities of daily living)	Hold dexamethasone until symptoms resolve. Restart with one dose level reduction. If symptoms persist despite above measures, discontinue dexamethasone do not resume.

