5.4 Stratification

Treatment allocation/randomization will be stratified according to the following factors:

1. Age (<75 vs. ≥75 years old)
2. International Staging System stage (ISS I or II vs. ISS III)

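### Time to first Grade 3-5 AE is compared without the age and ISS randomization strata; if those factors predict such events, the comparison is somewhat conservative, and stratifying costs almost nothing

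*Combined protocol and SAP*

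**What the plan says.** Section 5.4: "Treatment allocation/randomization will be stratified according to the following factors", namely age (<75 or ≥75) and ISS stage (I or II, or III), which gives four strata. Section 8.6.1 and Table 16 carry both factors into the comparisons of PFS, OS, PFS2, ORR and DCR.

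Section 8.6.2, under Time to Grade 3-5 AE, does not: "The treatment difference in time to first Grade 3-5 AE will be assessed by the unstratified log-rank test". For estimation: "The hazard ratio and its 95% confidence interval from the unstratified Cox model with a single treatment covariate will be reported". No reason is given for leaving the strata out.

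The same paragraph sets the status of the analysis: "In addition to tiered approach, exploratory analysis will be performed on time to first Grade 3-5 AE". It ends: "More details will be described in supplemental SAP". Elsewhere 8.6.2 names no Tier 1 events and rules out formal p-value comparisons for safety. No alpha, event target or power is attached to this endpoint.

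**The concern.** When allocation is balanced within strata and a stratum factor predicts the outcome, an analysis that ignores the strata has two known features.

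- **Test.** Balancing removes between-stratum variation from the treatment contrast, but the pooled log-rank variance still counts it. The test therefore rejects less often than its nominal level.
- **Estimate.** High-risk subjects leave the risk set earlier, and faster in the arm with the higher hazard. The pooled HR therefore lies nearer 1 than the HR within strata.

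In an efficacy analysis this caution guards against a false claim of benefit. For a harm endpoint it makes a real difference in toxicity a little harder to see. This is the one safety comparison in 8.6.2 for which a significance test is named, in a trial whose treatment phase was closed on safety grounds.

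**Working it through.** **1. The plan's own figures.** None exists for this endpoint, so the efficacy figures in Sections 8.1 and 8.9 were used to check the tools. Schoenfeld events for PFS: 4 × (1.960 + 1.282)² / (ln 0.65)² = 42.03 / 0.1856 ≈ 227, as stated; power at 227 events is 90.1%. For OS: Φ(√195 / 2 × |ln 0.70| − 1.960) = Φ(0.530) = 70.2%, against a stated figure of about 70%. Both reproduce.

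**2. Inputs.** From the documents: about 640 subjects, 1:1 allocation, four strata. Assumed, because the documents are silent:
- 40% aged ≥75 and 30% ISS III;
- 50% or 80% of subjects with a Grade 3-5 AE within a common follow-up;
- exponential times, and a within-stratum treatment HR of 1.0 or 1.30;
- HRs of 1 to 3 for age and 1 to 2 for ISS on Grade 3-5 AEs.

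**3. Method.** 1,500 simulated trials per setting, with allocation balanced within strata. Each trial was analysed both ways. At each event, p = n₁/(n₁ + n₀), with risk sets pooled or taken within stratum. The log-rank statistic is Z = Σ(A − p) / √Σp(1 − p), where A = 1 if the event is in the pembrolizumab arm. The Cox log-HR b solves Σ[A − n₁eᵇ/(n₁eᵇ + n₀)] = 0. Power is the share of trials with Z > 1.96.

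**4. Check on the simulation.** With non-prognostic strata, 50% of 640 is 320 events and Schoenfeld power at HR 1.30 is Φ(√320 / 2 × 0.2624 − 1.960) = Φ(0.387) = 65%. With 80%, 512 events give Φ(1.008) = 84%. The first row below agrees within simulation error.

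**5. Results at a true HR of 1.30** (unstratified → stratified):

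| Age HR / ISS HR | HR, 50% events | Power, 50% events | HR, 80% events | Power, 80% events |
|---|---|---|---|---|
| 1 / 1 | 1.305 → 1.305 | 66.6% → 66.2% | 1.304 → 1.303 | 84.6% → 84.6% |
| 1.25 / 1.25 | 1.302 → 1.304 | 65.2% → 65.5% | 1.298 → 1.302 | 83.6% → 84.1% |
| 1.5 / 1.5 | 1.296 → 1.303 | 64.9% → 66.1% | 1.288 → 1.302 | 82.4% → 84.0% |
| 2 / 1.5 | 1.287 → 1.303 | 63.1% → 65.7% | 1.275 → 1.302 | 79.8% → 84.1% |
| 2 / 2 | 1.280 → 1.304 | 61.6% → 65.9% | 1.266 → 1.303 | 76.9% → 83.3% |
| 3 / 2 | 1.263 → 1.304 | 56.9% → 66.1% | 1.242 → 1.302 | 70.4% → 84.1% |

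**6. Under the null**, the two-sided rejection rate across all settings was 2.2-5.4% unstratified and 4.1-5.8% stratified. With 1,500 runs the simulation error around 5% is ±1.96 × √(0.05 × 0.95 / 1500), about 1.1 points. The unstratified test never exceeds its level beyond that error, and it falls below it when the factors are strong.

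**The case against.** The strongest defence is that nothing here is broken. The analysis is labelled exploratory and sits outside the tiered approach. The unstratified test is valid, and its HR is a legitimate marginal estimate; the gap from the stratified HR reflects a different estimand. The Tier 2 intervals in 8.6.2 are not described as stratified either, so the safety section is consistent with itself. Safety is analysed by treatment received, and detail is left to a supplemental SAP that is not available here.

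Most of this stands, and it limits the weight of the point. It does not explain why the strata are dropped. Every subject in the as-treated population was randomized and so has a stratum, and the supplemental SAP adds detail to an analysis already specified as unstratified.

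A reader might also infer that the age-related dexamethasone recommendation makes matters worse: "For subjects aged > 75 years in both arms, a daily dexamethasone dose of 20 mg on days 1, 8, 15, and 22". The documents do not support that. The recommendation covers both arms, so it does not confound the comparison. It could narrow or widen the age difference in AE risk, and the documents do not say which. Its cut (>75) also differs from the stratum cut (≥75), so stratifying would not cleanly separate the dose groups.

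**Conclusion.** The point holds as a conditional and minor one. If age or ISS predicts Grade 3-5 AEs, the specified analysis is conservative and its HR lies nearer 1 than the within-stratum HR. At a true HR of 1.30 the difference is negligible for factor HRs up to 1.5. At 2 each it is 4-6 power points; losses of 9-14 points, with an HR of 1.24-1.26, appear only at factor HRs of 3 and 2. These sizes rest on the assumed stratum shares, event fractions and factor effects. The event fraction matters, because fewer events, as may follow from early closure of treatment, shrink the effect.

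A reader might infer that the toxicity HR will be biased and power lost as a matter of course. The documents do not support this. They report no effect of age or ISS on these events, no power was planned for the endpoint, and the test does not exceed its nominal level. The PFS and OS conclusions are not touched.

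**What to change.** In Section 8.6.2, or in the supplemental SAP, specify the log-rank test and Cox model for time to first Grade 3-5 AE as stratified by age (<75, ≥75) and ISS (I/II, III), using the strata applied at randomization. Report the unstratified result beside it as supportive. Safety data have already been reviewed by the DMC, so showing both avoids any appearance of choosing the model after the fact. Section 8.0 already allows the analysis to be modified and reported in the CSR.

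No new data are needed. If the strata turn out not to be prognostic, the cost is at most about one power point (66.6% against 66.2% in the first row of the table). The stratified HR is a conditional estimate that assumes one treatment HR across the four strata, and the report should say so.
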